#### **5.1.2 Subject Inclusion Criteria**

In order to be eligible for participation in this trial, the subject must:

1. Acute Myeloid Leukemia (AML), Acute Lymphoblastic Leukemia (ALL) or Myelodysplastic Syndrome (MDS) in confirmed relapse based on bone marrow examination after allogeneic HCT. Biopsy confirmed myeloid sarcoma or extramedullary AML may also be considered.
2. Confirmation of 'measurable disease' by blast % will be defined as a marrow blast percentage of > 5% by morphologic assessment on bone marrow examination. This criterion does not apply to myeloid sarcoma, or extramedullary leukemia, which must also show measurable lesion by CT, MRI, PET/CT or photograph (i.e. Leukemia cutis). If marrow blasts of ≤ 5% blasts are enumerated the patient may be eligible only if there is clear (probable or definite) flow cytometric, cytogenetic or molecular aberrations (e.g. FLT3-ITD, NPM1, etc.) documenting relapse of the leukemia associated clone defined prior to HCT.
3. Patient may not have received definitive salvage chemotherapy for their post-transplant relapse within the past 21 days. Use of hydroxyurea is permitted.
4. Be willing and able to provide written informed consent/assent for the trial
5. Be ≥ 18 years of age on day of signing informed consent
6. Be willing to provide tissue from bone marrow biopsies
7. Have a performance status of 0, to 1 on the ECOG Performance Scale. For purposes of HCT, this will correspond to a Karnofsky Performance status of ≥ 80%

8. Demonstrate adequate organ function as defined in Table 1, all screening labs should be performed within 10 days of treatment initiation

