### 8.2.2 Sample size estimate to assess if study drug is promising for further study

Considering the highly refractory nature of the subjects to be enrolled in this study and our lack of understanding of the kinetics of response to pembrolizumab in the post HCT setting, the investigators will be cautious about the potential underestimation of response of this novel agent. In addition, several, but not all patients are expected to receive standard chemotherapy at some point during their on-study therapy, thereby potentially confounding interpretation of the response rate to study drug. Therefore, the following criteria will be used to assess if the study drug is promising for further study:

(a) if  $\geq 4$  subjects demonstrate evidence of clinical benefit the drug will be considered promising. With 20 subjects we would be 90% confident that the true clinical benefit rate (CBR) lies between 7% and 40%. The CBR will be assessed on both day 35 and day 77 as determined by the proportion of subjects who receive pembrolizumab monotherapy who achieve either stable disease (SD) or ORR prior to the addition of standard chemotherapy

(b) the observation of any CRs seen in subjects not receiving standard chemotherapy will be considered promising.

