#### 8.2.2.1 Definition of Response.

For the purposes of this study, complete remission (CR) will be defined as achieving a morphologic leukemia free state by achieving all of the following criteria: bone marrow myeloblasts  $< 5\%$  by morphologic assessment; AND absence of circulating blasts with phenotypic or morphologic features of leukemia (e.g. Auer rods) AND no evidence of extramedullary disease. For subjects with  $\leq 5\%$  blasts but possessing flow cytometric, cytogenetic or molecular aberration (Sec 5.1); CR will also require resolution (absence) of that aberration. Partial remission (PR) will be defined as a  $\geq 50\%$  reduction in bone marrow blast percentage to 5-25% or marrow blasts  $< 5\%$  with persistent Auer rods, flow cytometric or cytogenetic disease. PR is not possible response designation for individuals entering with  $\leq 5\%$  blasts. SD will be defined as  $\leq 5\%$  increase in blasts or decreased blast percentage in the bone marrow that does not meet the criteria for PR. Progression will be defined as  $>5\%$  increase in bone marrow blast percentage from prior bone marrow aspirate. NOTE Given these patients have relapsed after allogeneic HCT blood count recovery is not considered at criteria for response in this protocol.

8.2.3 Stopping rules for futility: Study subjects will receive pembrolizumab  $\pm$  the addition of standard chemotherapy, therefore stopping rules for futility are not indicated. The primary endpoint of this study is safety and feasibility.

8.2.4 Stopping rules for toxicity: Patients will be monitored closely for the development of immune-mediated toxicity that may be attributable to pembrolizumab. For the purposes of this trial, we will consider the development of acute GvHD as a distinct entity from the known immune-mediated toxicity profile associated with PD1 blockade, though there may be clinical overlap. The impact of PD1 blockade on the development of acute GvHD following allogeneic HCT has not been studied in human subjects. Therefore, a rational approach will focus on whether there is an **increase** in the rates and severity of

acute GvHD and other immune mediated toxicities over the expected baseline. The following assumptions will be used to assess potential toxicities associated with this trial:

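### A subject entering with ≤5% marrow blasts can rise past the protocol's own 5% measurable-disease line, to at most 6–10% at day 35, and still count as clinical benefit

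*Combined protocol and SAP*

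**What the plan says.** Section 5.1.2, item 2, defines measurable disease as a "marrow blast percentage of > 5% by morphologic assessment on bone marrow examination". It also lets in subjects at or below 5% if a flow cytometric, cytogenetic or molecular aberration documents relapse.

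Section 8.2.2.1 gives these low-burden entrants two rules of their own. CR also requires the aberration to disappear, and "PR is not possible response designation for individuals entering with" blasts at or below 5%. For SD and progression there is no special rule. SD is a rise of no more than 5%, worded as "increase in blasts or decreased blast percentage in the bone marrow that does not meet the criteria for PR". Progression is a rise of more than 5%, worded as "increase in bone marrow blast percentage from prior bone marrow aspirate".

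Section 8.2.2(a) counts as clinical benefit those monotherapy subjects "who achieve either stable disease (SD) or ORR prior to the addition of standard chemotherapy". If at least 4 "subjects demonstrate evidence of clinical benefit the drug will be considered promising". Section 4.2.2 lists the clinical benefit rate (CBR) at days 35 and 77 among the primary efficacy endpoints.

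**The concern.** The plan recognises that low-burden entrants need their own response criteria, but it stops after CR and PR. For someone who enters above 5%, a rise of up to 5 points is a change within measurable disease. For someone who enters at or below 5%, the same rise can be the step from relapse seen only by flow, cytogenetics or molecular testing to relapse that is measurable by the protocol's own threshold. The plan scores that step as stable and counts it as benefit.

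At stake is the meaning of the go rule. Part of the count of 4 could come from subjects whose leukemia became measurable while on the drug.

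**Working it through.** **Inputs.** N = 20, threshold 4, and a 90% interval of 7% to 40% (8.2.2). SD and progression margin of 5% (8.2.2.1). Measurable disease above 5% (5.1.2). Units of the margin (5.2.1.2).

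**1. The plan's own figure.** The plan states: "we would be 90% confident that the true clinical benefit rate (CBR) lies between 7% and 40" per cent. The exact (Clopper-Pearson) 90% interval for 4/20 has lower limit Beta(0.05; 4, 17) = 7.1% and upper limit Beta(0.95; 5, 16) = 40.1%. The figure reproduces. The point below concerns who is counted among the 4, not this arithmetic.

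**2. Units.** Section 5.2.1.2 speaks of an increase in absolute marrow blasts. It offers 9% to 15% as an example of minimal progression. That is +6 points, just over a 5-point margin, but a relative rise of 6/9 = 67%, which would hardly be minimal against a 5% relative limit. So the margin is read as points. If it were relative, entry at 4% would be SD only up to 4 × 1.05 = 4.2%, and the point would fall away.

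**3. Ceiling for SD at day 35.** The ceiling is entry value + 5 points. The prior marrow is then the pre-treatment marrow, so the choice of reference does not matter.

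| Entry blasts | Highest value still SD | Above 5%? |
|---|---|---|
| 0% | 5% | no |
| 1% | 6% | yes |
| 2% | 7% | yes |
| 3% | 8% | yes |
| 4% | 9% | yes |
| 5% | 10% | yes |

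The affected window is therefore above 5% and up to 6–10%, depending on entry. Entry at 3% rising to 9% (+6) or at 2% rising to 20% (+18) is already progression, as is any low-burden entrant above 10% at day 35.

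**4. Day 77.** Measured from pre-treatment (5.2.1.2), the same ceilings apply. Measured from the prior aspirate (8.2.2.1), a second step is allowed: 4% to 9% to 14% is SD at both visits, whereas from pre-treatment 14% is +10 points and progression. That conflict is a separate matter. The defect exists under either reference.

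**5. Link to the go rule.** Four subjects in the window give 4/20 = 20% and meet 8.2.2(a) with no CR or PR in anyone.

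**6. Can the size be computed?** Let k low-burden entrants each be scored SD or better with probability p1, and the other 20 − k with probability p0. Then P(go) = P[Bin(k, p1) + Bin(20 − k, p0) ≥ 4]. The documents give none of k, p1 and p0, so every value here is an assumption. With k = 0, P(go) is 0.016 at p0 = 0.05 and 0.133 at p0 = 0.10. The last two columns suppose that 10 or 20 points of p1 lie in the window and are removed by the definition change.

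| k, p0, p1 | As written | 10 points removed | 20 points removed |
|---|---|---|---|
| 3, 0.05, 0.50 | 0.171 | 0.121 | 0.080 |
| 5, 0.10, 0.70 | 0.838 | 0.730 | 0.607 |

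The definition change alone lowers P(go) by 0.050 to 0.091 in the first row and by 0.108 to 0.231 in the second. Between 30/50 = 60% and 60/70 = 86% of the assumed SD stays. The rest of the gap from the k = 0 values comes from low-burden subjects who remain at or below 5%, which is not a scoring error.

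**The case against.** The strongest reply is that the 5% line in 5.1.2 is an eligibility definition, not a progression threshold. Low-burden entrants already have documented relapse, and one uniform margin is a design choice: 9% to 14% is SD as well. Changing it makes 5% to 6%, a single point, fail SD. That stands as a real cost of the change. It does not remove the inconsistency, because 8.2.2.1 itself already departs from uniform criteria for this group, and only these entrants can change disease category within the margin.

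The setting is also soft. Section 8.2.1 calls the analysis descriptive, 8.2.3 puts safety and feasibility first, 8.2.2 says the criteria guard against underestimating response, and ORR is reported separately. This lowers the severity. However, 8.2.2(a) still sets a numeric criterion for calling the drug promising, and caution about missing activity is a reason to count SD, not to count a move into measurable disease.

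Two stronger readings are tempting and not supported. A reader might infer that any low-burden subject who goes into overt relapse is scored stable; step 3 shows that only a bounded window is affected. A reader might also take the rise in P(go) from 0.133 to 0.838 as the effect of the flaw. It compares enrolling five low-burden subjects with enrolling none, on assumed rates, and much of it would survive the correction. Nor do the documents show that SD is the usual outcome in this group.

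**Conclusion.** The point holds in bounded form. On the absolute-point reading, a subject entering at 1–5% blasts can reach 6–10% at day 35, cross the protocol's measurable-disease line, be scored SD and count toward the 4 of 20. This follows from the text and needs no assumed rates. How often it would happen, and how far it would move the go decision, cannot be determined: the share of ≤5% entrants and the share landing in the window are both missing. The illustrative probabilities show only that the decision is sensitive to the low-burden group as a whole. Severity is moderate: the go rule should be made interpretable, but the trial's safety aims and its ORR estimates do not depend on it.

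**What to change.** In 8.2.2.1, for endpoint scoring only, state that for subjects entering with ≤5% marrow blasts, SD (and so clinical benefit) requires blasts to remain ≤5%. Name the endpoint category for those who exceed 5% by a rise of no more than 5 points, so that nobody is left unclassified. Apply the count of 4 in 8.2.2(a) on that definition, and report CBR separately for ≤5% and >5% entrants so that the decision can be read without the low-burden group. The split is needed as well as the definition, because most of the assumed low-burden SD in step 6 is untouched by the definition.

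Leave the treatment criteria in 5.2.1.2 unchanged. Say explicitly that the endpoint definition does not govern treatment, since Section 4.2.2.1 links SD at day 35 to continuing therapy. The differing reference marrows in 8.2.2.1 and 5.2.1.2 need to be reconciled separately.

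The cost is one or two sentences and an extra table row, with no new data or procedures. The downsides are a somewhat lower CBR, a small tolerance for entrants near 5%, and an endpoint category that can differ from the 5.2.1.2 label for the same subject. The change should be made before the count is applied; afterwards it would be a post hoc reclassification.

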#### 5.2.1.2 Dose Modification (Escalation/Titration/Other)

After initiated study treatment, the use of chemotherapy prior to day 35 bone marrow biopsy (or two cycles of pembrolizumab) is discouraged.

- Systemic Chemotherapy may be instituted in the following scenarios:

- Evidence for progressive AML or MDS on day 35 bone marrow biopsy. Progression will be defined as a minimum of > 5% increase in the absolute marrow blasts from pre-treatment biopsy. For example, increase in bone marrow blast from 10% on pretreatment biopsy to 25% on day 35 marrow examination OR

- At the discretion of the treating physician for impending rapidly progressive relapse (e.g. rapid increase in peripheral blast % or hematologic instability. These situations should be discussed in consultation with the study PIs OR
- Alternatively, subjects with minimal progression may remain on monotherapy if deemed there may be potential for subsequent clinical response or deemed poor candidates for systemic chemotherapy. For example, a subject who is tolerating pembrolizumab at day 35 of treatment with increase in bone marrow blasts to 15% at day 35 from 9% at pre-treatment will be recorded as progression but may remain on monotherapy to complete four dose of induction (phase I) at investigator's discretion.

- The chemotherapy regimen will be at the discretion of the treating physician and may include hypomethylation therapy or cytotoxic chemotherapy including high dose ara-C (e.g. FLAG) and/or anthracycline-based regimens. Other investigational agents are not permitted or the subject will be removed from further pembrolizumab and placed into follow-up.

Adverse events (both non-serious and serious) associated with pembrolizumab exposure may represent an immunologic etiology. These adverse events may occur shortly after the first dose or several weeks after the last dose of treatment. Pembrolizumab must be withheld for drug-related toxicities and severe or life-threatening adverse events (AEs) as per Table 3 below. Pembrolizumab must also be permanently discontinued in patients who develop  $\geq$  Grade 3 acute GvHD requiring systemic corticosteroids. Pembrolizumab should be temporarily held if acute GVHD grade II occurs. Pembrolizumab may be re-initiated once acute GVHD improves to < grade II. See Section 5.4 for supportive care guidelines, including use of corticosteroids.

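### Section 8.2.2.1 leaves the reference marrow for day-77 response open and judges stable disease on marrow alone, so clinical benefit and response rates can be biased up or down

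*Combined protocol and SAP*

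**What the plan says.** Section 8.2.2.1 gives the response definitions:

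- Progression is a more than 5% "increase in bone marrow blast percentage from prior bone marrow aspirate".
- SD is an at most 5% "increase in blasts or decreased blast percentage in the bone marrow that does not meet the criteria for PR". No reference marrow is named.
- PR is an at least 50% "reduction in bone marrow blast percentage to 5-25% or marrow blasts" below 5% with residual disease features. No reference marrow is named. The only hint is the exclusion "PR is not possible response designation for individuals entering with" 5% blasts or fewer.
- Extramedullary disease appears only under complete remission (CR): "AND no evidence of extramedullary disease".

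Section 5.2.1.2, writing about the day-35 marrow, measures progression as a more than 5% "increase in the absolute marrow blasts from pre-treatment biopsy". Its example is a subject whose "increase in bone marrow blasts to 15% at day 35 from 9% at pre-treatment will be recorded as progression but may remain on monotherapy" for the rest of induction.

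Section 8.2.2 counts SD, as well as response, as clinical benefit on monotherapy. It calls the drug promising if (a) at least 4 subjects show benefit, or (b) any CR occurs without chemotherapy. It adds that "The CBR will be assessed on both day 35 and day 77", but not which visit feeds the count of 4. Section 4.2.2.1 lists CBR and ORR among the primary efficacy endpoints. Section 5.1.2 allows entry with extramedullary disease on a measurable lesion, without the marrow-blast criterion.

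**The concern.** A response category needs a stated comparator. By day 77 a subject has two earlier marrows, pre-treatment and day 35, and the definitions do not say which one governs. The same three blast counts can then be benefit, progression, both or neither, depending on who classifies them. The situation is foreseeable: Section 5.2.1.2 expressly lets a subject recorded as progressing at day 35 reach day 77 on monotherapy.

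The extramedullary gap is separate and applies at both visits. These subjects enter on a lesion, yet SD and progression look only at marrow blasts. At stake are a listed primary endpoint and one of the two criteria for calling the drug promising.

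**Working it through.** **1. The plan's own figure.** The exact (Clopper-Pearson) 90% interval for x of n runs from the 5th percentile of Beta(x, n−x+1) to the 95th percentile of Beta(x+1, n−x). For 4/20 this is 7.1% to 40.1%, which reproduces the 7% to 40% in Section 8.2.2. For 3/20 (15%) it is 4.2% to 34.4%.

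**2. Four readings at day 77.** The 5% is taken as absolute points, as in Section 5.2.1.2.

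- A: progression, SD and PR all from the day-35 marrow.
- B: progression from day 35; SD and PR from pre-treatment.
- C: all from pre-treatment.
- D: progression and SD from day 35; PR from pre-treatment.

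Paths are blast percentages at pre-treatment/day 35/day 77; PD is progression.

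| Path | Change from day 35 | Change from pre-treatment | A | B | C | D |
|---|---|---|---|---|---|---|
| 10/15/20 | +5 | +10 | SD | none | PD | SD |
| 9/15/19 | +4 | +10 | SD | none | PD | SD |
| 40/18/18 | 0 | −22 (55% reduction) | SD | PR | PR | PR |
| 20/8/14 | +6 | −6 (30% reduction) | PD | SD and PD | SD | PD |
| 60/10/20 | +10 | −40 (67% reduction) | PD | PR and PD | PR | PR and PD |

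Reading A credits the first two rows with benefit at 10 points above pre-treatment. It also takes PR from 40/18/18 (lowering ORR but not CBR), SD from 20/8/14, and PR from 60/10/20, all with blasts below pre-treatment. Readings B and D, which mix references, give 60/10/20 two labels.

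I checked every whole-number path with pre-treatment 6–100, day 35 0–100 and day 77 5–100. A and C always give exactly one blast-change label. B leaves gaps and overlaps, and D leaves overlaps. This shows what is logically possible, not how often it would occur.

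**3. Does the visit matter?** Take reading A now and pre-treatment reference after the fix, and ask whether the subject counts as benefit (now → after).

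| Path | Day 35 only | Day 77 only | Either visit | Both visits |
|---|---|---|---|---|
| 10/15/20 | yes → yes | yes → no | yes → yes | yes → no |
| 9/15/19 | no → no | yes → no | yes → no | no → no |

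**4. Effect on the at-least-4 criterion.** One subject in 20 is 1/20 = 5 points. Assume exactly one subject is wrongly counted as benefit and the other 19 benefit independently with probability p. That subject decides criterion (a) only if exactly 3 of the others benefit: P(X = 3) = C(19,3) p³(1−p)¹⁶, with C(19,3) = 969.

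- p = 0.10: 969 × 0.001 × 0.9¹⁶ = 0.18
- p = 0.15: 969 × 0.003375 × 0.85¹⁶ = 0.24
- p = 0.20: 969 × 0.008 × 0.8¹⁶ = 0.22

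Outside this range it is smaller: 0.05 at p = 0.05, 0.09 at 0.30 and 0.02 at 0.40.

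The overall verdict flips less often, because any chemotherapy-free CR already meets criterion (b). If a share s of benefits are such CRs (an assumption), multiply by (1−s)³. At p = 0.15 the 0.243 becomes 0.177, 0.102 or 0.072 for s = 10%, 25% or one third.

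**5. Extramedullary disease.** Put Section 5.1.2 (entry on a lesion) beside Section 8.2.2.1 (SD and progression by marrow blasts). A subject with a growing lesion and an unchanged marrow meets SD at day 35 and at day 77. If entry blasts are 5% or fewer, PR is barred, so shrinkage short of CR is also SD. The efficacy rows of the flow chart in Section 6.0 are all marrow tests. Its closing note lets these be missed in myeloid sarcoma without a deviation, and no rule says how such a subject is classified.

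**The case against.** Several points on the other side stand. The analysis is declared descriptive (Section 8.2.1), and Section 8.2.3 calls safety and feasibility the primary endpoint. Extramedullary subjects only may be considered for entry, so there may be none. The 10/15/20 path is SD at day 35 on every reading, and it changes the count only if day 77 is used alone or both visits are required. Reading A is strained for PR, since a response simply held from day 35 would drop to SD.

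Three stronger inferences are tempting but not supported:

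- *That the wording inflates clinical benefit.* It can, but the last three rows of the first table go the other way. The documents give no blast trajectories from which a net direction could be derived.
- *That Sections 5.2.1.2 and 8.2.2.1 contradict each other.* Section 5.2.1.2 concerns the day-35 marrow, where the prior marrow is the pre-treatment one and the two agree. They part only if the day-35 wording is carried to day 77.
- *That the promising verdict is unreliable.* The flip probabilities are conditional on exactly one misclassified subject, and criterion (b) can make a flip irrelevant.

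None of this supplies the missing reference marrow or a lesion rule for SD.

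**Conclusion.** The point holds as a defect of definition that should be fixed. Day-35 marrow labels are sound. Day-77 labels depend on an unstated choice among at least four readings, so day-77 CBR and ORR can move in either direction. Extramedullary-only subjects can count as benefit on marrow alone at either visit.

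The size is 5 points of CBR per affected subject. One wrongly counted subject turns 3/20 into 4/20, with probability 0.18 to 0.24 of deciding criterion (a) if the true CBR in the others is 10% to 20%, and lower for the overall verdict. This rests on 5% meaning absolute points, independence between subjects, and exactly one affected subject. The actual number is not in the documents and may be zero.

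**What to change.** For response classification in the analysis only:

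1. In Section 8.2.2.1, measure PR, SD and progression at both visits from the pre-treatment marrow, with SD and progression in absolute percentage points. For subjects entering with more than 5% blasts, the blast-change categories then neither overlap nor leave gaps. If a rise from the day-35 marrow is also of interest, report it separately.
2. In Section 8.2.2, state which visit or visits feed the count of at least 4.
3. Do not count extramedullary-only subjects as SD on marrow alone. Keep them in the denominator, and count them as benefit only if an available lesion assessment shows no growth, by a stated criterion. Report those without an assessment separately as not evaluable for benefit.

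The cost is wording, with no new marrow, scan or visit. CBR and ORR may shift slightly either way, and extramedullary-only subjects without a lesion assessment will not count toward the 4.

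The labels also have effects outside the analysis: Section 5.2 and the Section 6.0 footnotes tie maintenance and later follow-up to them, and Section 5.6 ties disease-status follow-up to progression. The new text should say that it governs analysis only, and the investigators should reconcile those sections with it. No change to clinical management is proposed.

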**Table 2 Trial Treatment**

Drug	Dose/Potency	Dose Frequency	Route of Administration	Regimen/Treatment Period	Use
Pembrolizumab (Phase I: Induction)	200 mg	Every 3 weeks	IV infusion	Day 1 of each 3 week cycle x 4 doses	Experimental
Pembrolizumab (Phase II: Maintenance)	200 mg	Every 3 weeks	IV infusion	Day 1 of each 3 week cycle up to 13 doses	Experimental

**Description of Trial Treatment:** Eligible subjects will be initiated on pembrolizumab (phase I) for up to 4 doses with response assessments at day 35 (after 2 doses) and day 77 (after 4 doses). Subjects who are tolerating therapy without drug related adverse events (Table 3) AND who have disease in PR or CR on day 77 response assessment may be continued on pembrolizumab maintenance (phase II). Phase II treatment will continue for up to an additional 13 doses or until either toxicity or progression of malignancy at which time the subject will be placed into follow-up.

**Subjects initiated on systemic induction chemotherapy:** due to progression will receive no additional or concomitant phase I (induction) doses of pembrolizumab but may be considered for phase II maintenance pembrolizumab if disease assessment at day 77 (following chemotherapy) indicates PR or CR. Pembrolizumab may have synergistic effects with chemotherapy and/or facilitate augmentation of GVL after reduction of high leukemic burden.

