- All subjects will be inherently at risk for the development of GvHD as this study is limited to patients who have relapsed post-HCT. Although screening will exclude patients with active GvHD requiring immunosuppression, subjects will remain at risk independent of whether they receive study drug. The expected incidence of clinically significant grade 2 to 4 acute GvHD (requiring therapy) without Pembrolizumab is estimated to be 40-50%.
- Patients who relapse (without GVHD present) may still be receiving standard immunosuppression post-HCT to reduce the risk of inciting GVHD. Immunosuppressive medications (IS) may be withdrawn or tapered per usual care. Because patients are at risk for the development of GVHD within several weeks after IS withdrawal tapering may occur during administration of pembrolizumab at a rate determined by the treating physician. Due to timing of IS withdrawal overlapping with the treatment period for pembrolizumab, potentially confounding its relationship to the study drug, an aggregate summary of toxicity will be used to determine whether PD1 blockade is potentially associated with an increase in the severity of acute GvHD.
- For the purposes of this study, toxicity will be deemed as excessive if 12 of 20 subjects (60%) develop severe acute GvHD ( $\geq$  grade 3-4) OR  $\geq$  grade 3 immune related adverse events that do not improve to grade 1 after systemic corticosteroid treatment for 14 days. This study specific stopping rule is intended to capture excessive rates of severe acute GvHD (grades 3-4) as an adverse safety signal. We have set this threshold because some degree of GvHD is an anticipated consequence of usual withdrawal of immune-suppression and chemotherapy which is a current treatment standard for relapse. Grade 2 GvHD is associated with less morbidity and mortality compared to grades 3-4 and may be a potential surrogate of a beneficial anti-leukemic response (GvL), thus grade 2 GvHD will be recorded but not included in the stopping definition. The occurrence of severe acute GvHD for this toxicity rule will be monitored during the induction treatment period until 30 days after the last induction treatment dose of pembrolizumab given for the induction phase (doses 1-4).

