- We will also make interim assessments after 10 and 15 patients have been observed for 30 days after the last induction dose of pembrolizumab. Specifically, further accrual will be halted if we observe at least 6 of 10 or 9 of 15 patients developing severe acute GvHD. If the true rates of severe acute GvHD are 30%, 40%, 50% or 60%, the study has respective probabilities of 0.05, 0.18, 0.43, and 0.71 of stopping early.
- 

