### **10.5.2 Clinical Monitoring Plan**

This trial will be monitored in accordance with the NCI approved University of Michigan Comprehensive Cancer Center Data and Safety Monitoring Plan.

The study team will provide continuous review of the data and patient safety and meet monthly or more frequently depending on the activity of the protocol. The discussion will include matters related to the safety of study participants (SAE/UaP reporting), validity and integrity of the data, enrollment rate relative to expectations, characteristics of participants, retention of participants, adherence to the protocol (potential or real protocol deviations) and data completeness. At these regular meetings, the protocol specific Data and Safety Monitoring Report form will be completed and signed by the Principal Investigator or by one of the co-investigators.

Data and Safety Monitoring Reports will be submitted to the University of Michigan Comprehensive Cancer Center Data and Safety Monitoring Committee on a monthly basis for independent review.

The University of Michigan Comprehensive Cancer Center Data and Safety Monitoring Committee can request a 'for cause' audit of the study if the committee identifies a need for a more rigorous evaluation of study-related issues. A "for cause" audit would be conducted by the Quality Assurance Review Core (QARC) of the University of Michigan Comprehensive Cancer Center.

A regulatory authority (e.g. FDA) may also wish to conduct an inspection of the study, during its conduct or even after its completion. If an inspection has been requested by a regulatory authority, the site investigator must immediately inform the Clinical Trials Office that such a request has been made.

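### The severe acute GvHD halt in 8.2.4 waits for complete follow-up of 10 or 15 subjects even when the boundary is already reached; halting at that moment leaves the stopping probabilities unchanged and enrols somewhat fewer patients

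*Combined protocol and SAP*

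**What the plan says.** Section 8.2.4 of the combined protocol and SAP sets two looks: "We will also make interim assessments after 10 and 15 patients have been observed for 30 days after the last induction dose of pembrolizumab". At those looks, "further accrual will be halted if we observe at least 6 of 10 or 9 of 15 patients developing severe acute GvHD". The end-of-trial criterion is that "toxicity will be deemed as excessive if 12 of 20 subjects (60%) develop severe acute GvHD"; the same sentence also covers severe immune-related events that persist despite steroids. For true severe GvHD rates of 30, 40, 50 and 60%, 8.2.4 reports that "the study has respective probabilities of 0.05, 0.18, 0.43, and 0.71 of stopping early".

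The same section counts severe acute GvHD from the start of induction until 30 days after the last induction dose. The flow chart in Section 6.0 puts dose 4 on D64. Subjects who start systemic chemotherapy for progression "will receive no additional or concomitant phase I (induction) doses of pembrolizumab" (Section 5.2, below Table 2), so their window closes sooner.

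Safety is also reviewed between looks. Section 10.5.2 says: "The study team will provide continuous review of the data and patient safety and meet monthly" or more often, with monthly reports to the cancer center's monitoring committee. Section 10.5.3 adds a monthly review by the transplant program's own committee. Section 7.2.3.1 requires SAE reports to the sponsor within 24 hours. Section 5.8 allows early termination for a potential health hazard. None of these carries a GvHD count that triggers a halt.

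**The concern.** The rule is evaluated on completed follow-up. If the sixth severe case occurs while some of the first ten subjects are still under observation, the result of the 10-subject look is settled, because a case cannot be undone. The text still lets enrolment run until the last of the ten finishes. The same holds for the ninth case among fifteen.

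Nothing in the remaining follow-up can alter the decision, so the wait yields no information relevant to it. It only adds patients to a treatment whose effect on acute GvHD after transplant 8.2.4 describes as unstudied in humans. In a 20-subject trial with safety as a stated primary endpoint, even one or two such patients matter.

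**Working it through.** **Inputs from the documents.** Boundaries 6/10 and 9/15 (8.2.4). Dose 4 on D64 (6.0). Window to 30 days after the last induction dose (8.2.4). 20 subjects over an estimated 2-year enrolment (1.0).

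**Window and accrual.** With all four doses the window closes on D64 + 30 = D94, which is 93 days after D1. If the last induction dose is on D22, it closes on D52, 51 days after D1. Planned accrual is 20/24 = 0.83 a month, so about 93/30.44 × 0.83 = 2.5 subjects enter during a full window.

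**Reproducing the stated probabilities.** With X the cases among the first 10 and Y those among the next 5,

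P(stop early) = P(X ≥ 6) + Σ over x ≤ 5 of P(X = x) · P(Y ≥ 9 − x).

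Only x = 4 and x = 5 contribute to the sum. At 50%: 0.3770 + 0.2051 × 0.0312 + 0.2461 × 0.1875 = 0.3770 + 0.0526 = 0.4295 (unrounded).

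| True rate | Stop at 10 | Stop at 15 | Total | Stated |
|---|---|---|---|---|
| 30% | 0.0473 | 0.0037 | 0.0510 | 0.05 |
| 40% | 0.1662 | 0.0200 | 0.1863 | 0.18 |
| 50% | 0.3770 | 0.0526 | 0.4295 | 0.43 |
| 60% | 0.6331 | 0.0763 | 0.7094 | 0.71 |

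The plan's figures hold; 0.186 would round to 0.19, which is trivial.

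**Halting when the count is reached.** A patient-by-patient recursion that stops at the 6th case within the first 10 subjects, or the 9th within the first 15, gives 0.0510, 0.1863, 0.4295 and 0.7094. These are identical, because both versions stop on the same event: at least 6 cases in the first 10 or at least 9 in the first 15. Only the timing differs.

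**How often the tenth subject is not needed.** Given a stop at 10, the sixth case lies among the first nine subjects with probability P(X₉ ≥ 6)/P(X₁₀ ≥ 6). This is 67% at a true rate of 50% and 76% at 60%.

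**Patients saved.** Calendar-time simulation, 20,000 runs. Assumptions: Poisson accrual at 20 per 24 months, never paused; onset uniform over the window; a 93-day window for everyone; nobody halts by discretion.

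| True rate | Mean enrolled, all trials: as written / immediate | Saving | Trials that stop: as written / immediate | Saving |
|---|---|---|---|---|
| 30% | 19.6 / 19.5 | 0.1 | 12.9 / 11.0 | 1.9 |
| 40% | 18.7 / 18.3 | 0.4 | 13.1 / 11.0 | 2.1 |
| 50% | 17.1 / 16.1 | 1.0 | 13.2 / 10.9 | 2.3 |
| 60% | 15.1 / 13.2 | 1.9 | 13.1 / 10.5 | 2.6 |

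Savings are taken before rounding. In trials that stop, the halt comes about 75 days earlier at 30 and 40%, about 85 at 50% and about 97 at 60%.

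**Sensitivity at 60%, saving over all trials (1.9 in the base case).**
- Accrual of 0.5 a month: 1.5. Accrual of 1.5 a month: 2.4.
- Every event on the last day of the window: 1.0.
- Windows of cases closing early because dosing stops: 1.6, with the halt about 83 days earlier.
- As the previous line, and half of all subjects stopping after dose 2 (assumed): 1.5, with the halt about 79 days earlier.

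**The case against.** The strongest reply is that nothing here is wrong. Fixed looks at 10 and 15 are a legitimate design, and their boundaries and probabilities agree with each other. That stands: this is a refinement.

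Second, the trial is not blind between looks. SAEs go out within 24 hours, the study team reviews continuously, two committees review monthly, and Section 5.8 permits termination. A reader might infer that enrolment would run on unnoticed; the documents do not support that. Any of these bodies could act early, and the simulation assumes none does. What remains is that such action would be discretionary, since none has a GvHD count to act on. Open accrual is itself inferred, from the absence of any stated pause and from the halt applying to further accrual.

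Third, a reader might take two to three patients as the expected saving. That figure applies only to trials that stop. Over all trials it is about 0 to 2, and at a true rate of 30% it is almost nothing.

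Fourth, 93 days does not apply to everyone. Section 5.2.1.2 ends dosing for grade 3 or higher acute GvHD requiring systemic steroids, and chemotherapy ends induction dosing. Both shorten windows and the saving, as the sensitivity figures show.

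Fifth, a loosely worded trigger would change the operating characteristics. Counting maintenance-phase cases, counting events instead of patients, or using a different set of ten would each break the equality. This is right and shapes the fix.

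**Conclusion.** The point holds as an improvement to a sound rule. The 8.2.4 boundaries and probabilities need no correction. A reader might infer that the rule is invalid or that the trial lacks safety oversight; neither follows from the documents. The defect is one of timing: the halt can wait for follow-up that cannot change the outcome.

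The absence of statistical cost is exact, provided the subjects counted and the counting window are fixed in advance. The benefit is modest and depends on assumed accrual, onset timing and no discretionary halt. It matters most where the rule matters most, at true severe GvHD rates of 50% and above.

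**What to change.** Add to 8.2.4:

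> Accrual is halted as soon as 6 of the first 10 evaluable subjects (in enrolment order, after any replacement under 5.7), or 9 of the first 15, have developed grade 3-4 acute GvHD with onset between dose 1 and 30 days after that subject's last induction dose. The formal reviews at 10 and 15 subjects are kept on the same sets of subjects.

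The sentence counts patients, keeps the existing window and ties the running count to the sets used at the formal looks. Define evaluable alongside it, and state that a subject already counted as a case is not later replaced; otherwise the count could fall and the equality would fail.

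The cost is one sentence in an amendment, fixing the sets of 10 and 15 by enrolment order, and a running count kept at the existing monthly review. No threshold, data collection or clinical rule changes. If the count is updated only at the monthly meeting, the halt comes on average about half a month later, or 0.5 × 0.83 ≈ 0.4 subject in a trial that stops. Most of the saving is therefore kept.
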